### **3. INTRODUCTION**

As per ICH E9 (1), the purpose of this document is to provide a more technical and detailed elaboration of the principal features of the analysis described in the protocol, and to include detailed procedures for executing the statistical analysis of the primary and secondary variables and other data.

This trial statistical analysis plan (TSAP) assumes familiarity with the Clinical Trial Protocol (CTP), including Protocol Amendments. In particular, the TSAP is based on the planned analysis specification as written in CTP Section 7 “Statistical Methods and Determination of Sample Size”. Therefore, TSAP readers may consult the CTP for more background information on the study, e.g., on study objectives, study design and population, treatments, definition of measurements and variables, planning of sample size, randomisation.

Study data will be stored in a trial database within the Oracle ClinicalTM (O\*C) system.

Pharmacokinetic (PK) parameters will be calculated using Phoenix WinNonlinTM software (version 6.3 or higher, Certara USA Inc., Princeton, NJ, USA).

The statistical analyses will be performed within the validated working environment CARE, including SAS® (current Version 9.4, by SAS Institute Inc., Cary, NC, USA), and a number of SASTM-based tools (e.g., macros for the analyses of AE data or laboratory data; Report Appendix Generator system (RAGe) for compilation/formatting of the CTR appendices).

#### **4. CHANGES IN THE PLANNED ANALYSIS OF THE STUDY**

All analyses as planned in the CTP will be performed and are described in more detail in this TSAP. The following changes compared to the protocol will be made:

According to the Reference Document 3 of the Boehringer Ingelheim (BI) Statistical Position Paper on Statistical Methods for PK (13), the 90% confidence intervals (CI) should be considered for all described PK analyses. Therefore, the 90% CI will be used instead of the 95% CI.

## **5. ENDPOINTS**

### **5.1 PRIMARY ENDPOINT**

**Section 5.2.1 of the CTP:** *Primary endpoint to assess safety and tolerability of BI 1358894 is the number [N (%)] of subjects with drug- related adverse events.*

### **5.2 SECONDARY ENDPOINTS**

#### **5.2.1 Key secondary endpoints**

This section is not applicable as no key secondary endpoints have been defined in the CTP.

#### **5.2.2 Secondary endpoints**

##### **Section 5.5.1.1 of the CTP:**

- *AUC0-tz (area under the concentration-time curve of the analyte in plasma over the time interval from 0 to the last quantifiable data time point  $t_z$ )*
- *AUC0-∞ (area under the concentration-time curve of the analyte in plasma over the time interval from 0 extrapolated to infinity)*
- *Cmax (maximum measured concentration of the analyte in plasma)*

## 6. GENERAL ANALYSIS DEFINITIONS

### 6.1 TREATMENTS

It is planned that 64 healthy male subjects will enter the SRD part (8 per dose group, 6 on active and 2 on placebo) and 24 healthy males will enter the FE part (12 per dose group, all on active) of the study.

For details of dosage and formulation see Tables 6.1:1 and 6.1:2 below.

Table 6.1: 1 Labels for treatments for use in the CTR (SRD Part)

Treatment		Short label
P*	Placebo, tablet, qd	Placebo
AA	BI 1358894, 3*1 mg tablet, po, qd	BI 3mg
CA	BI 1358894, 6*1 mg tablet, po, qd	BI 6mg
AB	BI 1358894, 2*5 mg tablet, po, qd	BI 10mg
AC	BI 1358894, 1*25 mg tablet, po, qd	BI 25mg
AD	BI 1358894, 2*25 mg tablet, po, qd	BI 50mg
AE	BI 1358894, 1*100 mg tablet, po, qd	BI 100mg
AF	BI 1358894, 2*100 mg tablet, po, qd	BI 200mg
CD	BI 1358894, 2*100 mg tablet, po, qd, fed	BI 200mg fed

\*: The placebo control group in the safety evaluation will consist of all placebo treated subjects, regardless of the dose group in which they were treated.

Table 6.1: 2 Labels for treatments for use in the CTR (FE Part)

Treatment		Short label
W	BI 1358894, 2*25 mg tablet, po, qd, fed	BI 50mg fed
X	BI 1358894, 2*25 mg tablet, po, qd, fasted	BI 50mg fast
Y	BI 1358894, 1*100 mg tablet, po, qd, fed	BI 100mg fed
Z	BI 1358894, 1*100 mg tablet, po, qd, fasted	BI 100mg fast

The following separate study phases will be defined for the analyses of AEs:

- **Screening** (ranging from 0:00 h on day of informed consent until administration time of study drug)

- **On treatment**

(SRD part: separately for each treatment, ranging from the time of first administration of BI / Placebo until 0:00h on the day after trial termination date;

FE part: separately for each treatment, ranging from the time of first administration of BI until administration time of next study drug dose or 0:00h on the day after trial termination date)

Please note that all AEs reported between start of trial drug administration and the last per-protocol contact will be considered on treatment (i.e. no follow-up period is considered in this trial).

Displays of AEs will be presented separately for the treatments described in [Table 6.1: 1](#) and [Table 6.1: 2](#) above.

Two types of AE displays will be provided in the report:

**A)** Section 15.3 (separately for SRD and FE part) and Appendix 16.1.13.1.8 (for ClinicalTrials.gov and EudraCT only but combined for SRD and FE part) of the CTR displays:

In these displays, the on treatment phase will be analysed by dose group (labelled with the name of the study treatment (short label)). Screening will not be included in this analysis. The following totals will be provided in addition:

- a total over all on treatment phases included in this analysis ("Total on treatment") (Section 15.3 only)
- SRD part: a total over all BI treated phases ("BI Total")

**B)** Section 15.4 and Appendix 16.1.13.1.8 (except for ClinicalTrials.gov and EudraCT) of the CTR displays:

- Screening
- On treatment (labelled with the name of the study treatment (short label))

In Section 16.1.13.1.8 AE tables (separately for SRD and FE part), the following totals will be provided in addition:

- a total over all study phases ("Total")
- SRD part: a total over all BI treated phases ("BI Total")

Tables of vital signs and laboratory values will present results by the above mentioned screening and on treatment phase. Tables of ECG values will present results by the above mentioned on treatment phase

For detailed information on the handling of the treatments in the O\*C views refer to Technical TSAP ADS (analysis data set) plan and Analysis Data Reviewers guide.

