2. The time is approximate; the respective procedure is to be performed and completed within 2 h prior to drug administration. Allocation to treatment may be performed at any time following enrolment but must be completed prior to (first) drug administration.
3. If several actions are indicated at the same time point, the intake of meals will be the last action.
4. End of trial examination includes physical examination, body weight, vital signs, ECG, safety laboratory, recording of AEs and concomitant therapies, Bond & Lader and Bowdle visual analogue scales and suicidality assessment (C-SSRS).
5. Only urine drug screening and alcohol breath test will be done at this time point.
6. AEs and concomitant therapies will be recorded throughout the trial, but will be specifically asked for at the time points indicated in the [Flow Chart](#) above.
7. Safety laboratory to be taken and to be medically evaluated within 3 days prior to administration of study drug; this safety laboratory can be omitted, if the screening examination is performed on Days -3, -2 or -1.

14. Time points optional, may be modified after availability of PK data of each dose, EOT starts one day after the last ambulatory visit
15. Suicidality assessment only at screening and end of trial.
16. Confirmation of fitness includes physical examination, vital signs, ECG, recording of AEs and concomitant therapies. Evaluation of safety lab assessed on Day 2.

Proprietary confidential information © 2018 Boehringer Ingelheim International GmbH or one or more of its affiliated companies

Food Effect (FE), 50 mg and 100 mg

Visit	Day	Planned Time [h:min]	Approximate clock time of actual day [h:min]	Event and comment	Safety Laboratory	Alcohol and drug screening	PK _{blood} ^{9,12}	12-lead ECG	Vital signs (BP, PR, RR)	AE/CT-Questioning ⁶
1	-21 to -1			Screening examination ¹	x	x		x	x	
2 or 3 ⁸	-3	-72:00	8:00		x ⁷					x ⁷
	-1	-12:00	20:00	Admission to trial site	x ⁵					
1	-1:30	6:30		Treatment allocation ¹⁰	x ^{2,11}	x ²	x ²	x ²	x ²	x
				Standardized breakfast (only in fed state arm)						
	0:00	8:00		Drug administration						
	0:10	8:10				x				
	0:20	8:20				x				
	0:30	8:30				x				
	1:00	9:00				x		x		
	1:30	9:30				x				
	2:00	10:00		240 mL fluid intake		x	x	x	x	x
	2:30	10:30				x				
	3:00	11:00				x				
	4:00	12:00		240 mL fluid intake, Lunch ³		x	x	x	x	x
	5:00	13:00				x				
	6:00	14:00				x		x		
	7:00	15:00				x				
	8:00	16:00		Snack ³ (voluntary)		x	x	x	x	x
2	10:00	18:00		Dinner ³		x				

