3. DESCRIPTION OF DESIGN AND TRIAL POPULATION

3.1 OVERALL TRIAL DESIGN AND PLAN

This FIH study consists of an SRD and an FE part. The SRD part is designed as single-blind, partially randomised, and placebo-controlled within parallel dose groups, while the FE part will be conducted according to an open-label, randomised, two-way crossover design.

SRD:

The SRD part will start with a tablet formulation. In case the tablet formulation will be used up to the final dose group, 64 healthy male subjects will be included, according to 8 sequential groups comprising 8 subjects per group. However, based on in vitro data, there is a possibility that due to the low solubility of the drug substance and tablet, the exposure in subjects will be limited and increase may be less than dose proportional (see [Section 7.3.4](#)).

Further subjects may be entered to allow testing of additional doses on the basis of experience gained during the trial conduct (e.g. preliminary PK data), provided the planned and approved highest dose will not be exceeded. Thus, the actual number may exceed 64, but will not exceed 72 subjects entered. Such changes may be implemented via non-substantial CTP Amendments.

Within each dose group, 6 subjects will receive the active drug and 2 will receive placebo. Only one dose is tested within each dose group. Each dose group will consist of 3 cohorts which will be treated consecutively for safety reasons.

The dose groups to be evaluated are outlined in [Table 3.1: 1](#) below.

Table 3.1: 1 Dose groups (SRD part)

Test product 1: BI 1358894 tablets (1 mg, 5mg, 25 mg 100 mg)

*Administration under fed conditions

The dose groups of the SRD part will be investigated sequentially in ascending order of doses, maintaining a time interval of at least 5 days between the last drug administration in the previous dose group and the first drug administration of the subsequent dose group. The decision to proceed to the next dose group will be based upon the safety, tolerability, and exploratory pharmacokinetic data (see [Section 7.3.4](#)) of the preceding dose groups. The next

Proprietary confidential information © 2018 Boehringer Ingelheim International GmbH or one or more of its affiliated companies

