4.1.4 Drug assignment and administration of doses for each subject

The treatments to be evaluated are outlined in [Table 4.1.4: 1](#) below. The number of units // dose volume for placebo corresponds to the number of units // dose volume of the respective dose level.

Proprietary confidential information © 2018 Boehringer Ingelheim International GmbH or one or more of its affiliated companies

Table 4.1.4: 1 BI 1358894 and placebo treatments, oral administration for SRD part

Dose	Substance	Pharmaceutical form	Unit strength	Number of units / dose volume per administration	Total daily dose
1	BI 1358894	Film-coated tablet	1 mg	3 tablets	3 mg
2	BI 1358894	Film-coated tablet	1 mg	6 tablets	6 mg
3	BI 1358894	Film-coated tablet	5 mg	2 tablets	10 mg
4	BI 1358894	Film-coated tablet	25mg	1 tablet	25 mg
5	BI 1358894	Film-coated tablet	25 mg	2 tablets	50 mg
6	BI 1358894	Film-coated tablet	100 mg	1 tablet	100 mg
7	BI 1358894	Film-coated tablet	100 mg	2 tablet	200 mg
8*	BI 1358894	Film-coated tablet	100 mg	2 tablet	200 mg
1-8	Placebo*	Film-coated tablet	--	identical to active treatment	--

* Subjects receiving placebo are equally distributed across dose groups, dose group 8 treatment under fed conditions

Table 4.1.4: 2 BI 1358894 film-tablets for the FE part

Treatment	Substance	Pharmaceutical form	Unit strength	Number of units / dose volume per administration	Total Dose
T1 (tablet fed)	BI 1358894	Film-coated tablet	25 mg	2 tablets	50 mg
R (tablet fasted)	BI 1358894	Film-coated tablet	25 mg	2 tablets	50 mg
T1 (tablet fed)	BI 1358894	Film-coated tablet	100 mg	1 tablet	100 mg
R (tablet fasted)	BI 1358894	Film-coated tablet	100 mg	1 tablet	100 mg

The dose strengths to be tested will (lowest and highest dose) be re-evaluated after explorative safety and PK analysis.

The trial medication will be administered to the subjects, while they are in a sitting/standing position, as an oral dose together with about 240 mL of water, under supervision of the investigating physician or an authorised designee in the morning of Day 1. The so-called four-eye principle (two-person rule) should be applied for administration of trial medication and – if applicable – its preparation (e.g. reconstitution), if correct dosage cannot be ensured

Proprietary confidential information © 2018 Boehringer Ingelheim International GmbH or one or more of its affiliated companies

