The REP for BI 1358894, when measurable drug levels or PD effects are still likely to be present after the last administration, is not known for this first-in-human trial. Therefore, all AEs reported until the end of trial examination (last per protocol contact) will be considered on treatment (please see [Section 7.3.3](#)).

AE reporting to sponsor and timelines

The Investigator must report SAEs, AESIs, and non-serious AEs which are relevant for the reported SAE or AESI, on the BI SAE form via fax immediately (within 24 hours of awareness) to the sponsor's unique entry point (country specific contact details will be provided in the ISF). The same timeline applies if follow-up information becomes available. In specific occasions the Investigator could inform the sponsor upfront via telephone. This does not replace the requirement to complete and fax the BI SAE form.

With receipt of any further information to these events, a follow-up SAE form has to be provided. For follow-up information the same rules and timeline apply as for initial information.

Information required

For each AE, the investigator should provide the information requested on the appropriate eCRF pages and the BI SAE form, if applicable. The investigator should determine the causal relationship to the trial medication.

The following should also be recorded as an (S)AE in the CRF and BI SAE form (if applicable):

- Worsening of the underlying disease or of other pre-existing conditions
- Changes in vital signs, ECG, physical examination and laboratory test results, if they are judged clinically relevant by the investigator.

If such abnormalities already pre-exist prior to trial inclusion they will be considered as baseline conditions and should be collected in the eCRF only.

All (S)AEs, including those persisting after individual subject's end of trial must be followed up until they have resolved, have been assessed as 'chronic' or 'stable', or no further information can be obtained.

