7.3.3 Safety analyses

Safety will be assessed for the endpoints listed in [Section 5.2.1](#). All treated subjects (that is, all subjects who received at least one dose of study drug), will be included in the safety analysis. Safety analyses will be descriptive in nature and will be based on BI standards. No hypothesis testing is planned.

Treatments will be compared in a descriptive way. The placebo control group in the safety evaluation will consist of all placebo treated subjects, regardless of the dose group in which they were treated. The active treatment groups will be compared to the placebo group in a descriptive way. Tabulations of frequencies/proportions will be used for the evaluation of categorical (qualitative) data, and tabulations of descriptive statistics will be used to analyse continuous (quantitative) data.

In the SRD part, the active treatment groups will be compared to the placebo control group in a descriptive way. In the BA part, the two different treatments will be compared in a descriptive way. Tabulations of frequencies/proportions will be used for the evaluation of categorical (qualitative) data, and tabulations of descriptive statistics will be used to analyse continuous (quantitative) data.

The analyses will be done by 'randomised treatment'.

Proprietary confidential information © 2018 Boehringer Ingelheim International GmbH or one or more of its affiliated companies

Measurements (such as ECG, vital signs, or laboratory parameters) or AEs will be assigned to treatments (see [Section 4.1](#)) based on the actual treatment at the planned time of the measurement or on the recorded time of AE onset (concept of treatment emergent AEs).

Therefore, measurements planned or AEs recorded prior to first intake of trial medication will be assigned to 'screening', those between first trial medication intake until the end of trial visit will be assigned to the treatment period. These assignments including the corresponding time intervals will be defined in detail in the TSAP. Please note that AEs occurring after the last per protocol contact but entered before database lock will be reported to drug safety only and will not be captured in the trial database.

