## 7. PLANNED ANALYSIS

The SRD and FE part will be evaluated separately.

The placebo group in the safety evaluation of the SRD part will consist of all placebo treated subjects, regardless of the dose group in which they were treated.

Safety analysis (refer to [Section 7.8](#)) will be performed by and will be presented in Sections 15.1 to 15.4 of the CTR and in Appendix 16.2 and 16.1.13.1.

Inferential statistical analyses of PK endpoints (refer to [Section 7.5.2](#)) will also be performed by and will be presented in Section 15.5 of the CTR and in Appendix 16.1.13.3.

Descriptive data analysis of PK parameters and concentrations will be performed by the department of Translational Medicine and Clinical Pharmacology at BI and will be presented in Section 15.6 of the CTR.

The format of the listings and tables will follow the standards defined in the BI corporate guideline “Reporting of Clinical Trials and Project Summaries” [001-MCG-159] ([6](#)) with the exception of those generated for PK-calculations.

In the SRD part, the individual values of all subjects will be listed, sorted by treatment group, subject number, and visit.

In the FE part, the individual values of all subjects will be listed, sorted by treatment sequence, subject number, visit and actual treatment (if appropriate).

The listings will be included in Appendix 16.2 of the CTR.

For end-of-text tables, the set of summary statistics for non-PK parameters is:

N	number non-missing observations
Mean	arithmetic mean
SD	standard deviation
Min	minimum
Median	median
Max	maximum

For analyte concentrations, the following descriptive statistics will additionally be calculated:

CV	arithmetic coefficient of variation
gMean	geometric mean
gCV	geometric coefficient of variation

For PK parameters, the following descriptive statistics will additionally be calculated:

CV	arithmetic coefficient of variation
gMean	geometric mean
gCV	geometric coefficient of variation
P10	10th percentile

Q1	1st quartile
Q3	3rd quartile
P90	90th percentile

The data format for descriptive statistics of concentrations will be identical with the data format of the respective concentrations. The descriptive statistics of PK parameters will be calculated using the individual values with the number of decimal places as provided by the evaluation program. Then the individual values as well as the descriptive statistics will be reported with three significant digits in the CTR.

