### **7.8.1 Adverse events**

AEs will be coded with the most recent version of MedDRA.

The analyses of AEs will be descriptive in nature and will be based on BI standards as presented in the corporate guideline: “Analysis and Presentation of Adverse Event Data from Clinical Trials” [001-MCG-156] ([9](#)).

The standard AE analyses will be based on the number of subjects with AEs (and not on the number of AEs).

For analysis multiple AE occurrence data on the CRF will be collapsed into an AE provided that all of the following applies:

- All AE attributes are identical (lower level term (LLT), intensity, action taken, therapy required, seriousness, reason for seriousness, relationship, outcome, AE of special interest)
- The occurrences were time-overlapping or time-adjacent (time-adjacency of two occurrences is given if the second occurrence started within one hour after end of the first occurrence)

For further details on summarization of AE data, please refer to [001-MCG-156] ([9](#)).

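### SRD all-AE tables: 200 mg fed is planned to be observed about 1.8–2.6 times as long as pooled placebo, with no common AE window in the visible TSAP, so its any-AE count can be inflated by observation time alone

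*SAP*

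**What the plan says.** **AE window.** TSAP 6.1 assigns SRD AEs to the treatment for a period "ranging from the time of first administration of BI / Placebo until 0:00h on the day after trial termination date". Protocol 5.2.2.2 has the same rule and gives a reason: the residual effect period is unknown in this first-in-human trial, so "all AEs reported until the end of trial examination (last per protocol contact) will be considered on treatment". There is no separate follow-up phase. Protocol 7.3.3 leaves the detailed time intervals to the TSAP.

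**End of trial.** The flow chart for 3 mg to 200 mg fasted plans the end-of-trial examination for Day 10 to 14. Its footnote 14 makes this movable: "Time points optional, may be modified after availability of PK data of each dose, EOT starts one day after the last ambulatory visit". The separate chart for 200 mg fed plans it for Day 29 to 33, after ambulatory visits on Days 9, 11, 15, 22 and 29.

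**Columns and comparison.** Protocol 3.1: "Within each dose group, 6 subjects will receive the active drug and 2 will receive placebo". Footnote to Protocol Table 4.1.4: 1: "Subjects receiving placebo are equally distributed across dose groups, dose group 8 treatment under fed conditions". On pooling, TSAP 7 states: "The placebo group in the safety evaluation of the SRD part will consist of all placebo treated subjects, regardless of the dose group". Protocol 7.3.3: "The active treatment groups will be compared to the placebo group in a descriptive way". TSAP 7.8.1 bases the standard AE analyses on numbers of subjects with AEs and tabulates them by treatment.

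The visible TSAP has no common cut-off, no time-adjusted rate and no split by onset day. It refers to a company AE guideline (7.8.1) and a technical analysis-dataset plan (6.1), neither of which is available here.

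**The concern.** The proportion of subjects with at least one AE is cumulative, so it depends on how long each subject is watched. Here the length differs by column. The fed column has the long window. The fasted columns have the short one. The placebo column is a 14:2 mixture of the two.

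The 200 mg fed group was added under a raised exposure threshold, so it is where a reader will look first for a safety signal. With 6 subjects, one incidental late AE adds 16.7 points. A reader of the all-AE tables could not tell a drug effect from about three weeks of extra observation. Descriptive comparison is the only safety comparison planned, so the columns should mean the same thing.

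**Working it through.** **Counts.** 8 groups × 8 = 64 SRD subjects, which reproduces the planned number. Placebo: 8 × 2 = 16, of which 7 × 2 = 14 are in fasted groups and 2 in the fed group.

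**Window lengths.** With end of trial on day Ts (fasted) and Tf (fed), the mean placebo window is (14·Ts + 2·Tf)/16.
- Ts = 14, Tf = 29: 15.88 days; ratio 29/15.88 = 1.83.
- Ts = 12, Tf = 31: 14.38 days; ratio 2.16.
- Ts = 10, Tf = 33: 12.88 days; ratio 2.56.

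Counting exactly from 08:00 on Day 1 to 0:00 h after the end-of-trial day takes 8 h off each window and gives 1.84 to 2.60.

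**Size, illustration 1: shape of the hazard.** Assumptions, not from the documents: no drug effect; any-AE risk p = 20% by Day 12; Ts = 12; Tf = 31. A share f of the Day-12 cumulative hazard is front-loaded and the rest is constant. The decay uses k = ln 2/(40/24) per day, from the preliminary half-life of about 40 h in the Amendment 5 rationale.

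H(T) = −ln(1 − p)·[f·(1 − e^(−kT))/(1 − e^(−12k)) + (1 − f)·T/12]; risk(T) = 1 − e^(−H(T)); excess = risk(Tf) − [14·risk(Ts) + 2·risk(Tf)]/16.

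| f | Fed | Pooled placebo | Excess (points) | Of 6 subjects |
|---|---|---|---|---|
| 0 (constant) | 43.8% | 23.0% | 20.8 | 1.25 |
| 0.5 | 33.0% | 21.6% | 11.4 | 0.68 |
| 0.75 | 26.8% | 20.9% | 6.0 | 0.36 |
| 1 (all early) | 20.1% | 20.0% | 0.1 | 0.01 |

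Over the whole planned ranges of Ts and Tf, the constant-hazard excess is 16.4 to 25.3 points. It also depends on p: with the exact windows at mid-range, p = 5% gives 12.6 − 6.0 = 6.6 points and p = 40% gives 73.9 − 44.2 = 29.7.

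**Size, illustration 2: AEs in proportion to questionings.** The fasted chart shows 18 post-dose AE questionings to Day 9 plus end of trial = 19. The fed chart has no Day 8 (168 h) row. If it otherwise matches to Day 9 (an assumption, because the extracted table is damaged), it has 17. Days 11, 15, 22 and 29 plus end of trial add 4 or 5, since end of trial may fall on Day 29. The total is 21 or 22.
- 21: fed risk 1 − 0.8^(21/19) = 21.9%; placebo (14 × 20.0 + 2 × 21.9)/16 = 20.2%; excess 1.6 points.
- 22: fed risk 1 − 0.8^(22/19) = 22.8%; placebo 20.3%; excess 2.4 points.

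**If footnote 14 was used** (constant hazard, Tf = 31). A later fasted end of trial shrinks the gap: Day 21 gives ratio 1.39 and excess 10.0 points; Day 25 gives 1.20 and 5.8. An earlier one widens it: for Day 9 the mean placebo window is (14 × 9 + 2 × 31)/16 = 11.75 days, the ratio 31/11.75 = 2.64, and the excess 24.8 points.

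**BI Total against placebo.** The long-window share is 6/48 = 12.5% on active and 2/16 = 12.5% on placebo. At constant hazard both columns give 23.0%, a difference of 0.

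**The case against.** The best defence is that the rule is pre-specified and reasoned: with an unknown residual effect period, counting to last contact is the cautious choice, and any bias runs against the drug. The 200 mg fed group has its own labelled column. Individual data and dosing times will be listed and AE onset is recorded, so time to onset can probably be derived. No hypothesis is tested. The larger figures need a constant hazard after a single dose, although AE questioning is concentrated in the first three days. Company standards not seen here may already deal with the matter.

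Much of this stands as a limit on size. The 50%, 75% and 100% front-loaded cases and the questioning-based case all give less than one subject in six. None of it makes the columns comparable, and a reader of the tables would have to rebuild the comparison from listings. Footnote 14 also cuts both ways: the fasted end of trial may have moved later or earlier, so Day 10 cannot be taken as common to all groups without checking.

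A reader might go further and infer that the primary endpoint or the overall active-versus-placebo comparison is biased, or that the long fed follow-up is an error. The documents do not support this. Judging relatedness weighs the time to onset (Protocol 5.2.2.1), so late incidental AEs should rarely count as drug-related, although the investigator knows the treatment. BI Total and placebo have the same long-window share. The longer follow-up is extra safety monitoring; the gap is only in how the counts are presented.

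**Conclusion.** The point holds for the SRD all-AE tables, as a minor but cheap improvement. As planned, the 200 mg fed column is observed about 1.8–2.6 times as long as pooled placebo, and the visible TSAP sets no common AE window. The direction is certain: longer observation can only keep or raise the count. The size is unknown, because neither an AE rate nor the actual end-of-trial days are given. At an assumed 20% risk by Day 12 with no drug effect, it lies between about 0 and about 21 points, the top being the extreme of the hazard shapes tried; scaling with questionings gives about 1.6–2.4 points. The effect concerns one active column of 6 subjects in a descriptive analysis. It is probably near zero for drug-related AEs and absent from BI Total against placebo. Confidence is medium, because the company AE guideline and the technical dataset plan were not available.

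**What to change.** In TSAP 6.1 and 7.8.1:
- Keep the full-window tables.
- Add one supplementary SRD all-AE table that counts only AEs with onset from dosing to a single common cut-off.
- Define the cut-off as the earliest scheduled end-of-trial day among the SRD groups, under the schedules actually implemented after any footnote 14 change. This is Day 10 if the flow chart was unchanged. The window ends at 0:00 h on the following day. Individual early withdrawals do not move it; those subjects stay in the denominator with the data they have.
- List later-onset AEs by group with onset day.
- Footnote each group's actual follow-up (median and range).

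A matching drug-related table is optional, since little effect is expected there.

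The cost is one table, one listing and a footnote from data already collected. Real late AEs will appear only in the full-window tables and the listing. The cut-off does not remove the difference in in-house observation (at least 144 h for 200 mg fed, at least 48 h for the fasted groups).
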